### **7.2 Discontinuation Visits and Follow-up Procedures**

For Subjects discontinued due to adverse events, the clinical course of the event will be followed according to accepted standards of medical practice until the event resolves, stabilizes, or in the opinion of the Investigator, is no longer considered clinically significant.

### **7.3 Replacement of Discontinued Subjects/Specimens**

Recruitment of 146 Subjects is anticipated to accommodate potential subject attrition.

### **7.4 Retention of Data from Discontinued Subjects/Specimens**

No data will be collected from Subjects/specimens after the point of discontinuation except as needed to follow ongoing adverse events. All study data collected from the Subject up to the point of discontinuation will be recorded on the Case Report Form, entered into the study database, and included in subsequent analyses, as appropriate.

## **8.0 RISK / BENEFIT ASSESSMENT**

### **8.1 Potential Risks**

The risks to the Subject are non-significant and the findings may reveal information that may improve medical care for persons with diabetes. The potential benefit to medical practice outweighs the non-significant differential risk experienced by the study Subject compared with current standard of care. As a result of inserting a pen needle, Subjects may experience pain, bleeding, or local infection. However, given the size of the investigational pen needles (4mm x 32G or smaller) and the procedures being used in disinfecting the skin and pen devices prior to inserting the pen needle, these risks are negligible.

Risks associated with a pen needle injection may include:

- Discomfort or pain
- Fainting
- Bleeding
- Bruising
- Redness
- Infection

## 8.2 Potential Benefits

There are no direct benefits to the Subject for participation in this study. The findings may reveal information that will allow for a better understanding of pen needles, and thus may improve medical care for persons with diabetes.

## 9.0 SAFETY

### 9.1 Adverse Event Definitions

**Adverse Event (AE):** Any unfavorable and unintended sign (including an abnormal laboratory finding), symptom or disease in a Subject that is temporally associated with the use of an investigational product or procedures, even if the event is not considered to be related to the study product or procedures.

This includes events not seen at baseline and events that have worsened if present at baseline. The term AE will refer to all adverse events (serious and non-serious) occurring during participation in a study of either investigational devices and/or drugs.

**Serious Adverse Event (SAE):** An SAE is any AE occurring during study participation that results in any of the following outcomes:

- Death
- Life Threatening (refers to any event in which the Subject was at risk of death at the time of the event; it does not refer to an event which hypothetically might have caused death if it were more severe)
- Hospitalization or prolongation of a hospital stay
- Persistent or significant disability or incapacitation (refers to any event which results in a substantial and/or permanent disruption of the Subject's ability to carry out normal life functions)
- Required intervention to prevent permanent impairment/damage
- Congenital anomaly/birth defect
- Important medical event that may require intervention to prevent one of the preceding conditions.

**Unanticipated Adverse Device Effect (UADE):** Any serious adverse effect on health or safety or any life-threatening problem or death caused by, or associated with, a device, if that effect, problem, or death was not previously identified in nature, severity, or degree of incidence in the investigational plan or application (including a supplementary plan or application), or any other unanticipated serious problem associated with a device that relates to the rights, safety, or welfare

of Subjects (21CFR-812.3(s)). Refer to Protocol Section 8.1 (Potential Risks) for a list of *anticipated* adverse events, signs or symptoms.

### 9.2 Adverse Event (AE) Management

Each Subjects will be questioned in an open-ended manner throughout the conduct of the study as appropriate for any new or worsening undesirable signs or symptoms they may have experience since being exposed to the study product. Elicited signs and symptoms must be comprehensively documented on the appropriate source documentation.

Each sign, symptom, disease or illness reported must be evaluated by the Investigator or designee to determine if it meets the definition of an Adverse Event.

The clinical course of the event will be followed according to accepted standards of medical practice until the event resolves, stabilizes, or in the opinion of the Investigator, is no longer considered clinically significant. The Investigator must supply the Sponsor with information concerning the follow up and/or resolution of the AE.

Some reported or observed signs and symptoms are inherent to subcutaneous injection and are likely to occur transiently for nearly all Subjects in this study. Such signs or symptoms will not be considered AEs as long as they are mild (transient, easily tolerated, no interference with daily activities) and the Principal Investigator agrees. The following will not be considered AEs:

- Mild, self-limited pain, swelling at the injection site and presence of wheals
- Mild bruising at the injection site
- Mild self-limited bleeding at the injection site

However, these signs and symptoms **must be considered AEs and** documented on the Adverse Event CRF should any of them occur in such a way that the extent or nature of the experience exceeds that normally associated with the procedure, as judged by the Subject to be excessive pain, bruising or bleeding.

All needle breaking that results in a cannula remaining in the body either partially or fully, **must be considered an AE** and documented on the Adverse Event CRF.

### 9.3 Assessment of Adverse Events (AEs)

All AEs must be assessed for Seriousness, Severity, and Relationship. All AEs, regardless of classification, must be comprehensively documented in the CRF and on the SAE form, if applicable, and reported to BD. This includes AEs related to marketed study products. The following information about the event is to be reported on the AE CRF:

- Seriousness, classified as: Non-Serious or Serious
- Severity, classified as:
  - Mild: Transient symptoms, easily tolerated, no interference with daily activities
  - Moderate: Marked symptoms, moderate interference with daily activities, tolerable
  - Severe: Considerable interference with daily activities, intolerable
- Relationship to the study product or study procedures:
  - Not Related: Evidence suggests absolutely no possible causal relationship between the event and the investigational study device (or procedures).

- Unlikely Related: Evidence suggests that other possible causes or contributing etiological factors may have caused the event other than the investigational study device (or procedures).
- Possibly Related: Evidence suggests a causal relationship between the event and the investigational study device (or procedures) cannot be ruled out
- Related: Evidence suggests a reasonable causal relationship between the event and the device (or procedures) is likely

In addition, the following should be recorded for each AE:

- Action(s) taken to remedy the AE, including change in study treatment or participation, or medical/surgical treatments
- Duration of the AE from onset through resolution, as applicable
- Cause (including suspected product/procedure and/or other cause)
- Outcome of the event, including resolution and sequelae, as applicable

#### **9.4 Additional Procedures for Assessing & Reporting Serious Adverse Events (SAE)**

SAE criteria are specified in Section 9.1. All SAEs must also be assessed by the Investigator and Sponsor Medical Monitor to determine whether an SAE is expected or unexpected. An adverse event will be considered unexpected or unanticipated if the nature, severity or frequency of the event is not consistent with the risk information previously described in the protocol, Informed Consent, or Investigator's Brochure (if applicable).

Any adverse event meeting the criteria for 'Serious', regardless of the Investigator's opinion of expectedness or relationship to the study product, must be reported to BD within 24 hours. The Investigator or designee must report the event by telephone or email to the Study Monitor. In addition to reporting the SAE to the Study Monitor, the Investigator must also submit a completed SAE form to the BD Trial Safety Dept. via fax or email listed below within 24 hours of receipt of the information.

- Safety Email: [BD\\_Trial\\[contact]](mailto:[contact])
- Safety Fax Line: (US) [name]

Medical questions about study safety issues and serious adverse events can be directed to the Sponsor Medical Monitor.

##### **9.4.1 Reporting Obligations to IRB/EC and Health Authorities**

The Investigator must report any adverse events which are serious, unanticipated/unexpected and probably or possibly related to the study product or procedures to the reviewing IRB/EC. This report must be submitted as soon as possible, but in no event later than 10 working days after the Investigator first learns of the event.

The Investigator may also have additional responsibilities for AE reporting to their governing Health Authority which they are responsible for identifying and fulfilling.

The Sponsor will provide results of any evaluation of an unanticipated/unexpected adverse device effect to appropriate Health Authorities, to all Investigators, and to all reviewing

IRB/ECs within 10 working days after the Sponsor is notified of the event. If the Investigator wishes to assume responsibility for filing reports of evaluation results to their own IRB/EC in lieu of the Sponsor, they must notify the Sponsor in writing of this preference and must retain evidence of their compliance with this requirement.

BD will comply with all other Sponsor safety reporting requirements and timelines for other entities (e.g., Data Safety Monitoring Boards) and local health authorities in other countries where this study or other studies with the same product are being conducted, in compliance with study procedures and applicable local regulatory requirements and BD Standard Operating Procedures.

## 10.0 INCIDENTS

A Clinical Study Incident is defined as any problem or issue involving the investigational product(s), reference methods, associated procedures or equipment, or represents a product-related injury (or potential for injury) to study Subjects or personnel as a result of execution of this protocol. Clinical Study Incidents may adversely (or potentially adversely) affect human safety, the integrity of the evaluation data, or the operation of devices or systems, and warrant prompt attention.

Incidents involving injury to study Subjects will also be reported as Adverse Events (refer to Section 9). Examples of Clinical Study Incidents that are not Adverse Events might be **mislabeled or adulteration of the investigational device, equipment or device malfunctions, and errors in the device instructions, damage to devices caused by shipping or handling or improper storage, or injury to study personnel due to execution of the protocol**. If appropriate, an Incident may also be documented and reported as a protocol deviation.

Study-specific procedures for reporting Incidents, as well as adverse events and protocol deviations, will be provided to the study Site prior to study execution. The Monitor should be contacted immediately when the Site becomes aware of or suspects any defective or malfunctioning product. This includes:

- Products that are involved in Study Incidents,
- Products that are found to be expired, damaged or defective,
- Products that are possibly the cause of an adverse effect, regardless of whether the product was believed to be damaged, defective or malfunctioning.

Such products (whether investigational or marketed) should be segregated and returned with appropriate documentation to the BD address below, unless instructed otherwise by BD. The Study Monitor should be contacted with any questions regarding return of study products. BD will supply mailing kits specifically intended for product contaminated with potentially bio-hazardous material.

## 11.0 RETURN OR DESTRUCTION OF STUDY PRODUCT

Unless instructed otherwise by BD, the Investigator will return all used pen needles that are determined to have presence of bending (secured in the provided metal containers), unused or unopened test, reference, and ancillary study products to BD. At the conclusion of the study, and as appropriate during the course of the study, any products, supplies or BD equipment that are required to be returned will be shipped to BD at the address below, unless instructed otherwise:

---

[name]  
Becton, Dickinson and Company  
[name]  
[name]  
[contact]

### **11.1 Defective or Failed Study Products**

DFSP: The term DFSP generally refers to any damaged, malfunctioning, or failed product (confirmed or suspected) identified at the investigational Site. DFSP includes:

- Products that are involved in Study Incidents,
- Products that are found to be damaged or defective,
- Products that fail or malfunction during the study,
- Study products rendered unusable due to Subject/patient/Site staff mis-use or improper storage conditions,
- Products that are possibly the cause of an adverse effect, regardless of whether the product was believed to be damaged, defective or malfunctioning.

The Monitor must be contacted immediately when Site becomes aware of any DFSP. All DFSP (whether investigational or marketed) should be segregated and returned with appropriate documentation to the BD address above, unless instructed otherwise by BD. The Study Monitor should be contacted with any questions regarding return of study products. BD will supply mailing kits specifically intended for product contaminated with potentially bio-hazardous material.

Depending on the intended use of the study products in the study (e.g., if assessing failure modes), there may be exceptions or additions to the requirements for DFSP/Incident documentation; these will be described in this protocol or the study-specific Monitoring Plan.

## **12.0 DATA COLLECTION AND MANAGEMENT**

### **12.1 Source Documents**

Source data includes all information in original records (and certified copies of original records) of clinical findings, observations, or other activities (in a clinical study) used for the reconstruction and evaluation of the study. Source data are contained in source documents (original records or certified copies) and are used to verify the authenticity of information recorded on the Case Report Form (CRF). Typical source documents include the hospital chart, medical office file, laboratory report, clinician notes, patient record, recorded data from automated instruments or other documentation prepared and maintained by the investigator/staff or ancillary services which contains a record of all observations and other data pertinent to the investigation on a study Subject.

The investigator is required to maintain original source documents at the site. Should an original source document (e.g., an instrument printout, direct entry CRF) need to be forwarded to BD for data entry, the site must retain a clearly designated certified copy. The Study Monitor will confirm that procedures for copy certification have been established at the site prior to transmittal of any original source documents.

## **12.2 Case Report Forms (CRF)**

The case report forms (CRF) will be provided by the Sponsor. The term “CRF” as used in this protocol may refer to traditional paper CRFs, or electronic case report forms for electronic data capture (EDC), as determined by the Sponsor.

The Investigator may delegate CRF completion to study personnel. However, the Sponsor must be apprised in writing of the name of such persons and the scope of their authority. The Principal Investigator or designee is obligated to review each CRF page and sign or initial the indicated pages using ink or for EDC, an electronic signature. An individual record will be kept for each Subject that provided informed consent.

All entries to a paper CRF should be made clearly in black or dark blue indelible ballpoint pen to ensure the legibility of self-copying or photocopied pages. Corrections are made by placing a single horizontal line through the incorrect entry, so that the original entry can still be seen, and placing the revised entry beside it. The revised entry must be initialed and dated by a member of the Investigator's research team authorized to make CRF entries. Correction fluid must not be used.

CRF entries will be compared to source documents by the study monitor or designated personnel. Unless specified otherwise, all information on the CRFs must be traceable to original source documents.

### **12.2.1 CRF as Source Document**

In this study, the following CRFs may serve as original source documents:

- Visual Analog Scale for pain
- 5-Point Likert for thumb force
- Demographics/Diabetes History
- Subject Questionnaire(s)

### **12.2.2 CRF/Data Transmittal**

Instructions for CRF Transmittal will be provided to the site at Study Initiation. Specific procedures may be described in a study-specific Monitoring Plan.

## **12.3 Data Management and Storage**

Data Management will be performed by the Sponsor. Data from completed CRFs will be entered into a controlled database and the database verified for accuracy against the CRFs, when applicable. If electronic data capture is utilized, the electronic records entered at the site will be entered directly into the controlled database. Data security is ensured through password protection, limited access, audit trails, and regular backups of the data. Upon completion of the study and verification of data, data will be screened for accuracy and completeness, after which the database will be locked from any additional changes. A copy of the locked database will be provided to the GCD Statistics Department for statistical analysis.

### 13.0 STATISTICAL METHODS

Statistical methods will be detailed in a Statistical Analysis Plan. Any deviations from the original statistical plan will be justified and described in an amended statistical analysis plan and/or the protocol, or in the final statistical report and clinical study report.

#### 13.1 Sample Size Determination

**Pain:** Assuming the SD for relative VAS is ~50mm (based on DBC-17NUCLS07), a sample size of 266 pairs per each comparator has >90% power of passing a -10mm NI criteria, assuming no true difference in pain (based on a 2-sided 95% CI for the mean).

**Leakage:** Based on previous study data (BDT-2P00116) where leakage  $\geq 1.5U$  was observed in 66/298 (22.1%) of injections performed with Artsana 34G, in 25/299 (8.4%) of injections performed with Comfort EZ 33G, in 19/296 (6.4%) of injections performed with Artsana 33G and in 3/297 (1%) of injections performed with BD Nano™ PRO, a simulation was performed (code found in SVN repository under DBC-18PENDL01\Stat\Sample Size\Bayesian prior proportion R) indicating that 798 injections with BD Nano™ PRO and 266 injections per each comparator would provide >90% power to show BD Nano™ PRO superiority to each comparator.

A 10% buffer was added (to compensate for subject attrition or unusable data), leading to a planned enrollment number of 146 subjects.

Table 1 summarizes the sample size scenario.

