## 3.0 STUDY DESIGN

### 3.1 Overall Study Design

This is a subject partially blinded, block randomized, prospective, single-visit, multi-center study to compare user experiences with BD Nano™ PRO pen needle vs. three (3) thinner commercially available comparator pen needles (Artsana Insupen Extr3me 33G, Artsana

Insupen Extr3me 34G and the Simple Diagnostics Comfort EZ™ 33G Pen Needles). The study will include up to 146 study subjects having Type 1 or Type 2 diabetes.

Study conduct will consist of one 60 to 120 minute Site visit in which pre-set doses of saline will be abdominally delivered by Subjects via a reusable insulin pen device. All pen needles will be attached by Study Staff and pen needle outer cover and inner shield will be removed for subjects. Subjects are to perform 12 injections into the abdomen (6 pairs of injections). Pairs of injections will be evaluated and each pair will contain one BD Nano™ PRO and one comparator pen needle. Within the 12 injections, each comparator will be injected twice, therefore each subject will experience 2 of each of the following pairs:

BD Nano™ PRO pen needle vs Artsana Insupen Extr3me 4mm x 33G x 2

BD Nano™ PRO pen needle vs Artsana Insupen Extr3me 3.5mm x 34G x 2

BD Nano™ PRO pen needle vs Simple Diagnostics Comfort EZ™ 4mm x 33G x 2

Subjects will not see pen needle labels or be informed which pen needle is being used to inject. The BD Nano™ PRO has a distinct configuration and subjects will most likely notice the difference vs the comparators. Subjects will not be informed of the BD's or the comparator's pen needle brand, length or gauge.

The pen needle order within the pairs of injections will be randomized for each subject and the pairs will be randomized to various abdominal injection sites within each subject.

Besides being informed of the requirement to insert the pen needles 'straight-in' (perpendicular), subjects will be instructed to use their usual injection technique.

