**Table 1. Sample size**

PN type	90% power for pain NI (based on pairs)		Power to show superiority (leakage $\geq 1.5U$ )	
	# of PNs	# of subjects (2 pairs per subject)	Sample size involved in comparisons	power
Artsana 33G	266	133	N = 266 Artsana 33G vs N = 798 BD Nano™ PRO	90%
Comfort EZ 33G	266	133	N = 266 Comfort EZ 33G vs N = 798 BD Nano™ PRO	98%
Artsana 34G	266	133	N = 266 Artsana 33G vs N = 798 BD Nano™ PRO	>99%
Total BD# PNs	798			
# Subjects		133		
# Subjects + 10% margin		146		

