### 13.3 Statistical Methods

Descriptive statistics (number of observations, mean, and standard deviation, minimum and maximum) will be calculated and presented for all quantitative responses. Frequency tables with number of observations, percentage of total and 95% confidence interval (score method) for the percentage (as applicable) will be created for discrete responses.

Analysis for relative VAS pain: For each comparator PN, a two-sided 95% confidence interval will be calculated for the average rating. A modeling approach may be used to adjust for the pair order effect, BD order effect within pair (due to the often-observed bias towards favoring the last pen needle used in a pair), abdomen site effect and random subject effect. Results will be tested for non-inferiority, followed by superiority:

If the lower bound of the CI is  $> -10\text{mm}$ , we can conclude in non-inferiority  
If the lower bound of the CI is  $> 0\text{mm}$ , we can conclude in superiority

Analysis for thumb force via 5-point Likert scale: For each comparator PN, the responses will be converted to ratings of  $-2 - 2$  (where positive ratings favor BD) and a two-sided 95% confidence interval will be calculated for the average rating. A modeling approach may be used to adjust for the pair order effect, BD order effect within pair, abdomen site effect and random subject effect. Results will be tested for superiority:

If the lower bound of the CI is  $> 0$ , we can conclude in superiority

Responses will also be converted to 3 categories: favoring comparator (negative ratings), no difference (0 ratings) and favoring BD Nano™ PRO (positive ratings) and the difference in percentage of responses with a preference for BD vs each comparator needle calculated, adjusting for the “no preference” category.

Analysis for needle bending and leaking: analysis will be performed using a binary logistic regression with random subject effect and fixed pen needle effect, pair order effect, PN order effect within pair and abdomen site effect. The average difference in percentage of occurrence with BD PN and each comparator PN will be calculated with 95% confidence interval and assessed for statistical significance. The upper bound of the confidence interval will be compared to 0: superiority will be concluded given that the upper bound of the 95% confidence interval for the difference in proportions is  $< 0\%$ .

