6.1 Derived Variables

6.1.1 Relative VAS Scale

After completion of each pair of injection, subjects will be asked to compare pain between the pen needles using a 150mm relative VAS Scale. Marks made on the 150mm relative VAS Scale are read using a 0 - 20 grid and the resulting discrete scores entered into the database. The results will be transformed to a [-75mm, 75mm] scale for analysis and reporting, where positive scores will reflect less pain for BD Nano Pro and negative scores will reflect less pain for comparator pen needle.

Subjects will draw a vertical line on a relative VAS scale for each pair of injections, to indicate their relative pain perception for the pen needle used first or second in the pair. A vertical line drawn to the left of the center mark indicates that the 1st injection was less painful. A vertical line drawn to the right of the center mark indicates that the 2nd injection was less painful. A vertical line drawn at the center mark indicates no difference. Figure 1 shows an example of a 150mm (may not be to scale) relative VAS scale.

Which injection was less painful?

The **1st injection** was much less painful.

No Difference

The **2nd injection** was much less painful.

Figure 1: VAS Scale for Injection Pain

The scores are entered into the database on a discrete 0 - 20 scale. These scores will be transformed to a 150mm VAS on a [-75mm, 75mm] scale as follows:

Let $Y_{recorded}$ (= 0, 1, ..., 20) be the recorded VAS score, the first transformation for the analysis of VAS score, $Y_{analusis}^*$ (mm), will be calculated as:

$$Y_{analysis}^* = \frac{150}{20} * Y_{recorded} - 75 \tag{1}$$

The sign of the VAS responses $Y_{analysis}^*$ will then be adjusted depending on which pen needle was used in the first and in the second injection, so that positive scores (+) will reflect less pain for BD Nano and negative scores (-) will reflect less pain for comparator pen needles. Let $Y_{analysis}$ be the final relative VAS score used for the analysis. Then:

$$Y_{analysis} = \begin{cases} Y_{analysis}^*, \text{ if BD Nano is provided in the 2}^{nd} \text{ injection} \\ -Y_{analysis}^*, \text{ if BD Nano is provided in the 1}^{st} \text{ injection} \end{cases}$$
(2)

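### The power above 90% for pain non-inferiority treats 266 ratings as independent, but they are two per subject from 133 subjects; at an SD of 50 mm, a within-subject correlation above about 0.013 takes it below 90%.

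*Protocol*

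**What the plan says.** Protocol 13.1 takes an SD of about 50 mm for the relative VAS from an earlier study (DBC-17NUCLS07) and concludes that "a sample size of 266 pairs per each comparator has >90% power of passing a -10mm NI criteria, assuming no true difference in pain", the criterion being "based on a 2-sided 95% CI for the mean". SAP section 3 gives the same figure.

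Table 1 of the Protocol heads the pain columns "90% power for pain NI (based on pairs" and "of subjects (2 pairs per subject", and lists 266 pen needles and 133 subjects for each comparator. Protocol 3.1 confirms the repetition: "therefore each subject will experience 2 of each of the following pairs". Enrolment is then raised to 146: "A 10% buffer was added (to compensate for subject attrition or unusable data").

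On the analysis, Protocol 13.3 says "A modeling approach may be used to adjust for the pair order effect, BD order effect within pair", with abdomen site and a random subject effect also listed. SAP 6.2.1 commits to such a model. Neither document gives a within-subject correlation, a design effect or an SD of subject means.

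**The concern.** The sample size section counts pairs as the independent unit, while the analysis section models pairs as clustered within subjects. If a subject who finds one needle less painful on the first pair tends to find it so on the second, the two ratings share information, and 266 ratings are worth fewer than 266 independent ones. A random subject effect describes that dependence but does not remove it: with balanced data, the standard error of a comparator's mean still carries the factor 1 + ICC.

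This is the only power figure given for the primary endpoint, and it was set with almost no slack. If non-inferiority is missed for a needle, a reader will ask whether the study really had 90% power. The documents as written do not secure that answer.

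**Working it through.** **Inputs from the documents.** SD 50 mm, true difference 0, two-sided 95% interval and 266 pairs per comparator (Protocol 13.1, SAP 3); margin -10 mm (Protocol 3.3); two pairs per comparator per subject and 133 subjects (Protocol 3.1, Table 1); 146 enrolled (Protocol 13.1). The ICC is not given, so every value below is an assumption.

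**1. The plan's own figure.** Power = Φ(10/SE − 1.96), with SE = 50/√266 = 3.066 mm. So 10/3.066 − 1.96 = 1.302, and power = 90.4%. A t interval on 265 degrees of freedom gives 90.1%. The stated figure is reproduced, under independence.

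**2. Slack under independence.** Pairs needed for 90% = (1.96 + 1.2816)² × 50²/10² = 262.7. The plan has 266, which is 1.3% more.

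**3. Two ratings per subject.** SE = 50 × √((1 + ICC)/(2 × subjects)). Power is exactly 90% when 1 + ICC = pairs/262.7:

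- 133 subjects: 266/262.7 − 1 = 0.013
- 146 subjects: 292/262.7 − 1 = 0.11

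**4. Power per comparator over assumed ICCs** (normal approximation):

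| ICC | 133 subjects | 146 subjects | Subjects needed for 90% |
|---|---|---|---|
| 0 | 90.4% | 92.8% | 132 |
| 0.1 | 87.5% | 90.3% | 145 |
| 0.3 | 81.6% | 85.0% | 171 |
| 0.5 | 75.9% | 79.7% | 198 |

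The last column is 262.7 × (1 + ICC)/2, rounded up; at ICC 0.05 it is 138. For example, at ICC 0.1 and 133 subjects, SE = 3.215 mm and 10/3.215 − 1.96 = 1.150, which gives 87.5%. At an assumed ICC of −0.1, power at 133 subjects is 93.0%.

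**5. Sensitivity to the SD.** At 133 subjects the ICC threshold is 0.054 if the SD is 49 mm and 0.099 if it is 48 mm. At 51 mm, power is 89.2% even with ICC 0.

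**6. If 50 mm is before order adjustment.** Take an assumed order bias of 15 mm, with order balanced. The adjusted SD is √(2500 − 225) = 47.7 mm, and 90% needs 239.0 pairs. The thresholds become 266/239.0 − 1 = 0.11 and 292/239.0 − 1 = 0.22. At ICC 0.1, power is 90.3% (133 subjects) and 92.7% (146).

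**7. Only if all three comparators must pass.** At ICC 0 the three results are independent in this model: 0.9035³ = 73.8% at 133 subjects, and 79.8% at 146. At ICC 0.1, a single subject intercept correlates the three comparator means at 2 × 0.1/1.1 = 0.18, which gives 69.1% and 75.2%.

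**The case against.** The strongest reply is that the 0.013 threshold is fragile and the real loss is unknown. The SD is only approximate, and a 1 mm change moves the threshold by several times its own size. Any sample size solved to just reach 90% will show a threshold near zero. The ICC could be small or negative. The rating compares two needles within a pair, and its sign "will then be adjusted depending on which pen needle was used in the first and in the second injection", so a habit of favouring the last needle enters with opposite signs when a subject's two pairs have opposite orders. Enrolment is 146 for a single visit, which holds 90% up to an ICC of about 0.11. Table 1 openly says that the power is based on pairs. The all-three figures rest on a reading that the decision rules, applied needle by needle in Protocol 13.3 and SAP 6.2.1, do not adopt.

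Much of this stands as qualification. The size of the loss cannot be known from the documents, and the figures at ICC 0.3 and 0.5 are illustrations. The all-three question is separate and conditional.

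It does not answer the point. The approximate SD cuts both ways: 51 mm misses 90% with no correlation at all. The buffer is assigned to attrition and unusable data; at ICC 0.1, 145 of the 146 subjects would have to be evaluable. Naming the unit as pairs does not disclose an assumption that the pairs are independent.

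**Conclusion.** The concern holds. The stated power is correct arithmetic for 266 independent ratings, but the design does not supply independent ratings. At 133 subjects and an SD of 50 mm, the claim has 0.4 percentage points of headroom, and any within-subject correlation above about 0.013 removes it. The shortfall is modest at an assumed ICC of 0.1 (87.5%) and material at 0.3 (81.6%). It could be absent if the ICC is zero or negative, or if order adjustment brings the SD sufficiently below 50 mm.

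The effect is on the power claim alone. Because SAP 6.2.1 models the subject effect, type I error and the intervals remain valid. The point should be corrected, but it does not threaten the analysis. Whether the primary objective needs all three comparators to pass is a gap in detail that the documents leave open; the conclusion does not depend on it.

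**What to change.** In Protocol 13.1, Table 1 and SAP section 3:

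- Restate the per-comparator power with variance SD² × (1 + ICC)/266. Take the ICC from DBC-17NUCLS07 if it can be estimated there; otherwise show the power over a stated range.
- Say whether the 50 mm SD is before or after adjustment for needle order.

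In the primary objective, say whether it makes three separate claims or requires all three comparators to pass. If all three are required, give that power as well.

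The cost is a few sentences and one table heading. No added enrolment is asked for, and nothing in the analysis or decision rule changes if the claims are separate. The restated power may look less favourable.
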